6.2 RESPONSE CRITERIA

6.2.1 Definitions

For the purposes of this study, patients will be evaluated for response every 4 weeks.

Response is defined by at least 50% reduction in TBSAI at week 12.

Partial Response is defined by 25-49% reduction in TBSAI at week 12.

No response to therapy is defined as stable or worsened (increase in total body surface area involvement) skin disease on anakinra.

Abbreviated Title: Anakinra in pustular dermatoses

Version Date: December 12, 2018

Other parameters used to assess disease response include American College of Rheumatology criteria and other clinical markers. ACR20/50/70 is defined as 20%, 50% and 70% improvement in tender or swollen joint counts, respectively.

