5. Joint Pain Visual Analog Scale is a self-administered psychometric response instrument which measures subjective characteristics or attitudes that cannot be directly measured. It ranges from 0-10. This scale has been used for measurement in a variety of dermatologic settings. This questionnaire will be administered at baseline, week 4, week 8, week 12 and week 16. (1 minute) (**APPENDIX H: PUSTULAR DERMATOSIS CLINICAL ASSESSMENT SCALE**)
6. Overall Disease Severity Visual Analog Scale is a self-administered psychometric response instrument which measures subjective characteristics or attitudes that cannot be directly measured. It ranges from 0-10. This scale has been used for measurement in a variety of health settings. This questionnaire will be administered at baseline, week 4, week 8, week 12 and week 16. (1 minute) (**APPENDIX H: PUSTULAR DERMATOSIS CLINICAL ASSESSMENT SCALE**)
7. Health Assessment Questionnaire (HAQ) is a self-administered questionnaire which aims to assess health-related quality of life longitudinally based on five patient-centered dimensions: disability, pain, medication effects, costs of care, and mortality. This instrument is used in the calculation of the ACR70. This questionnaire will be administered with each rheumatology evaluation. (5 minutes) (**APPENDIX I: HEALTH ASSESSMENT QUESTIONNAIRE**)

Completed questionnaires will be maintained in the subject's research chart until study analysis is completed.

Abbreviated Title: Anakinra in pustular dermatoses

[figure not shown]
Version Date: December 12, 2018

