6.2.2 Disease Parameters

Measurable disease: Total body surface area involvement of pustules and erythematous plaques will be measured in this study. At the time of enrollment, all study participants will have active disease warranting systemic therapy, as defined by macroscopic non-infective pustular and inflammatory skin lesions involving $\geq 5\%$ of the total body surface area, or palmoplantar involvement.

Joint involvement will also be assessed using criteria set forth by the American College of Rheumatology.

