6.2.4 Response Criteria

6.2.4.1 Evaluation of Target Lesions

TBSAI50 is defined as 50% improvement in total body surface area involvement.

ACR20/50/70 is defined as 20%, 50% and 70% improvement in tender or swollen joint counts and other clinical markers, respectively.

No response to therapy is defined as stable or worsened (increase in total body surface area involvement) skin disease on anakinra.

Abbreviated Title: Anakinra in pustular dermatoses

Version Date: December 12, 2018

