22 APPENDIX J: JOINT EXAM CLINICAL ASSESSMENT FORM

Pilot Study on Anakinra in Pustular Skin Disease: Joint Assessment

Visit Number		
Subject Initials	Subject ID	Visit Date

Joint exam

Instructions for each joint (box). Please only list joints affected by underlying inflammatory arthritis:

(1) Swollen joints

a. Fill in the box if there is swelling or effusion. R L
 b. Total number of swollen joints (regardless of tenderness): _____

(2) Tender joints

a. In the absence of swelling/effusion, place an "X" in the box if there is tenderness or painful ROM.
 b. Total number of tender joints WITHOUT swelling: _____

(3) Limited ROM

[figure not shown]
a. Circle each box where there is limited ROM.
 b. Total number of joints with limited ROM: _____

(4) Total number of active joints:

a. Add up #1 and #2, do NOT count joints with limited ROM but no swelling or tenderness

b. Total number of active joints: _____

(5) If any joints were NOT assessed, specify: _____

(6) If all joints were assessed and normal, check this box:

MD Signature _____

MD Name _____

Collection of this information is authorized under 42 USC 285. The primary use of the information you provide is to assess your health and quality of life. The information may be disclosed to clinicians and researchers for research purposes and to monitor personnel to assure that safety standards are maintained. Submission of this information is voluntary.

Abbreviated Title: Anakinra in pustular dermatoses

Version Date: December 12, 2018

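### With counts taken from Appendix J, joints that worsen from tender to swollen can meet the joint-count part of ACR20/50/70 under section 6.2.1

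*Combined protocol and SAP*

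**What the plan says.** The plan describes the joint response in several places, and they do not match.

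- **Section 6.2.1:** "ACR20/50/70 is defined as 20%, 50% and 70% improvement in tender or swollen joint counts, respectively". No other component is named.
- **Section 6.2.4.1:** the same thresholds, but now for "improvement in tender or swollen joint counts and other clinical markers, respectively". The markers are not listed.
- **Section 3.4**, on the HAQ: "This instrument is used in the calculation of the ACR70". It does not say how the HAQ enters, or whether it also enters ACR20 and ACR50.
- **Section 6.2.2:** "Joint involvement will also be assessed using criteria set forth by the American College of Rheumatology". The criteria are not written out.
- **Appendix J**, the only joint form shown: item 1 totals all swollen joints, tender or not. Item 2 is the "Total number of tender joints WITHOUT swelling". Item 4, the active joints, is formed by the instruction "Add up #1 and #2, do NOT count joints with limited ROM but no swelling or tenderness". There is no total of all tender joints, and neither ACR definition mentions item 4.

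Section 6.2.1 places ACR among the other response parameters. The primary measure is TBSAI50 (sections 1.1.1 and 8).

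**The concern.** On the form, the tender and swollen counts are mutually exclusive. A joint that changes from tender to swollen leaves one count and enters the other. A rule satisfied by a fall in either count can therefore be met by joints that have only changed category, and in this direction the change is for the worse.

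Rheumatologic manifestations and functional measures fall within the secondary objectives (section 1.1.2). The study calendar lists ACR assessment at baseline and at weeks 4, 8, 12 and 16. The group is small, so one wrong classification shows in the rate. The documents do not say how many patients will have joint disease. Assuming between 5 and all 25 evaluable patients, one misclassified patient moves the ACR response rate by 1/5 = 20 to 1/25 = 4 percentage points.

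**Working it through.** The plan states no figure that depends on the ACR rule, so there is none to reproduce. The check applies the Appendix J counting rules to illustrative patients.

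**Inputs.** Item 1 = swollen joints, tender or not. Item 2 = joints tender without swelling. Item 4 = item 1 + item 2. Thresholds of 20%, 50% and 70% come from sections 6.2.1 and 6.2.4.1. The joint patterns are assumptions.

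**Formula.** Improvement = (baseline count − follow-up count) / baseline count.

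**Tender joints becoming swollen.** Baseline is 10 tender-only joints and 0 swollen (item 1 = 0, item 2 = 10, item 4 = 10). At follow-up, k of them are swollen and still tender:

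| k | Item 1 | Item 2 | Item 4 | Fall in item 2 | Threshold met on item 2 |
|---|---|---|---|---|---|
| 2 | 2 | 8 | 10 | (10−8)/10 = 20% | 20% |
| 5 | 5 | 5 | 10 | (10−5)/10 = 50% | 50% |
| 6 | 6 | 4 | 10 | (10−4)/10 = 60% | 50% only |
| 7 | 7 | 3 | 10 | (10−3)/10 = 70% | 70% |
| 10 | 10 | 0 | 10 | (10−0)/10 = 100% | 70% |

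In every row item 4 changes by (10−10)/10 = 0%. A count of all tender joints, swollen or not, would also go from 10 to 10, or 0%. The swollen count rises from zero, so its percentage change is undefined.

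**Mixed baseline.** 6 tender-only and 4 swollen-and-tender joints become 10 swollen-and-tender joints. Item 2: (6−0)/6 = 100%. Item 1: (4−10)/4 = −150%. Item 4: (10−10)/10 = 0%. All tender joints: 10 to 10, 0%. An either-count rule scores this as a 70% response. A rule requiring both counts does not.

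**Opposite direction.** 10 swollen-and-tender joints become 10 tender-only joints. Item 1: (10−0)/10 = 100%. Item 4: 0%. Because item 1 ignores tenderness, its fall is a real loss of swelling and not a product of the form. Item 4 alone would give that no credit.

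**Applying each definition.** Under section 6.2.1, read as either count, the first two patterns can be scored as responses on joint counts alone. Under section 6.2.4.1 the joint-count part is met in the same way, but the unlisted markers must also improve. Under section 3.4, ACR70 also depends in some unstated way on the HAQ.

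**The case against.** The case against has four parts.

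1. **Other components.** Sections 6.2.4.1 and 3.4 bring in other markers and the HAQ, and section 2.4 describes the joint assessment as using ACR criteria with the HAQ. Joint counts alone then need not produce ACR70. This stands, and it is why the false response is only possible. It does not remove the problem: no marker, threshold or HAQ rule is given, so these sections supply no safeguard that can be computed.
2. **Wording.** The phrase in section 6.2.1 could mean one combined count of joints that are tender or swollen, which is item 4. All the examples above would then show 0%. The reading is open, but the text uses the plural, and the form gives the combined total a different name that neither definition uses.
3. **Source of the counts.** Nothing in section 6.2 names Appendix J. Section 6.2.3 refers to ACR guidelines, and section 6.1 says case report forms will be developed. The link is an inference, though a reasonable one, since no other joint form is shown.
4. **Weight.** ACR is supplementary, the rheumatology consultation is at the investigator's discretion (section 2.4), rheumatoid arthritis is excluded (section 2.1.2.16), and section 8 attaches no test or decision to ACR. Items 1, 2 and 4 are all recorded, so the shift can be seen in the data. This limits the consequence but leaves the scoring rule unsettled.

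**Conclusion.** The point holds in a conditional form. If either count suffices under section 6.2.1, and the counts come from Appendix J, then at least 20%, 50% or 70% of tender-only joints becoming swollen meets the joint-count part of ACR20, ACR50 or ACR70, with no fall in active joints. The sections also disagree on what else an ACR response requires.

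A reader might infer that any patient whose joints go from tender to swollen will be scored ACR70. The documents do not support that. It depends on the either-count reading and on the form as the source, it needs at least 70% of the tender-only joints to leave the count (60% reaches only the ACR50 threshold), and sections 6.2.4.1 and 3.4 add further components. A reader might also infer that a move from swollen to tender-only is an equally false response. It is not: swelling has resolved, and the most that can be said is that the either-count rule is lenient.

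The primary endpoint, the sample size and the early stopping rule are unaffected. The change is worth making because it is cheap and a stated rule can otherwise return the wrong direction.

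**What to change.** Write one identical ACR20/50/70 definition in sections 6.2.1 and 6.2.4.1, consistent with section 3.4. It should list every component, say how the HAQ and any other markers enter, require the stated percentage improvement in both the tender and the swollen count, and say how a baseline count of zero is handled. Name Appendix J as the source of the counts, and revise that form to mark and total tenderness in every joint, swollen or not. With these changes the tender-to-swollen patterns above give 0% improvement in the tender count and no response.

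On forms already completed, the tenderness of swollen joints cannot be recovered. For those, report the percentage change in item 4 alongside the swollen count as a joint-count response, and do not credit a fall in item 2 alone as improvement. Item 4 should not stand alone: it scores tender-to-swollen worsening as no change and gives no credit for resolved swelling. The swollen count beside it shows both.

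The cost is a small form revision, a change to the definition wording, and possibly lower joint response rates. The completed-form rule needs no new data, since items 1, 2 and 4 are already collected.

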6.2.2 Disease Parameters

Measurable disease: Total body surface area involvement of pustules and erythematous plaques will be measured in this study. At the time of enrollment, all study participants will have active disease warranting systemic therapy, as defined by macroscopic non-infective pustular and inflammatory skin lesions involving $\geq 5\%$ of the total body surface area, or palmoplantar involvement.

Joint involvement will also be assessed using criteria set forth by the American College of Rheumatology.

6.2.3 Methods for Evaluation of Measurable Disease

Plaque and pustular disease will be measured by Total Body Surface Area Involvement (TBSAI) as well as Physician Global Assessment (PGA). Additionally, Pustular Psoriasis Assessment Severity Index (PPASI) and Palmoplantar Psoriasis Assessment Severity Index (PPPASI) scores will be calculated for each patient (**APPENDIX H: PUSTULAR DERMATOSIS CLINICAL ASSESSMENT SCALE**). All baseline evaluations will be performed as closely as possible to the beginning of treatment and not more than 4 weeks before the beginning of the treatment. The same method of assessment and the same technique should be used to characterize skin lesions at baseline and during follow-up.

Clinical lesions: Skin lesions will be documented using clinical examination and disposable ruler as needed, and color photography (at the investigator's discretion). Joint lesions will be documented by clinical examination as delineated by ACR guidelines, and joint imaging modalities. Ocular involvement will be assessed through a comprehensive ophthalmic exam including assessment for keratoconjunctivitis. Ocular exams will occur in the eye clinic at baseline and at completion of the study unless otherwise medically indicated. Specialized ophthalmic testing (i.e., optical coherence tomography, fluorescein angiography, fundus photos or visual fields) will only be performed if medically indicated and required to establish a diagnosis.

Histology: Histologic evaluation will be used to diagnose and characterize disease at the time of enrollment and completion of anakinra.

6.2.4 Response Criteria

6.2.4.1 Evaluation of Target Lesions

TBSAI50 is defined as 50% improvement in total body surface area involvement.

ACR20/50/70 is defined as 20%, 50% and 70% improvement in tender or swollen joint counts and other clinical markers, respectively.

No response to therapy is defined as stable or worsened (increase in total body surface area involvement) skin disease on anakinra.

Abbreviated Title: Anakinra in pustular dermatoses

Version Date: December 12, 2018

7 SAFETY REPORTING REQUIREMENTS/DATA AND SAFETY MONITORING PLAN

7.1 DEFINITIONS

7.1.1 Adverse Event

Any untoward medical occurrence in a human subject, including any abnormal sign (for example, abnormal physical exam or laboratory finding), symptom, or disease, temporally associated with the subject's participation in research, whether or not considered related to the subject's participation in the research.

7.1.2 Suspected adverse reaction

Suspected adverse reaction means any adverse event for which there is a reasonable possibility that the drug caused the adverse event. For the purposes of safety reporting, 'reasonable possibility' means there is evidence to suggest a causal relationship between the drug and the adverse event. A suspected adverse reaction implies a lesser degree of certainty about causality than adverse reaction, which means any adverse event caused by a drug.

7.1.3 Unexpected adverse reaction

An adverse event or suspected adverse reaction is considered "unexpected" if it is not listed in the investigator brochure or is not listed at the specificity or severity that has been observed; or, if an investigator brochure is not required or available, is not consistent with the risk information described in the general investigational plan or elsewhere in the current application.

"Unexpected" also refers to adverse events or suspected adverse reactions that are mentioned in the investigator brochure as occurring with a class of drugs or as anticipated from the pharmacological properties of the drug, but are not specifically mentioned as occurring with the particular drug under investigation.

7.1.4 Serious

An Unanticipated Problem or Protocol Deviation is serious if it meets the definition of a Serious Adverse Event or if it compromises the safety, welfare or rights of subjects or others.

7.1.5 Serious Adverse Event

An adverse event or suspected adverse reaction is considered serious if in the view of the investigator or the sponsor, it results in any of the following:

- Death
- A life-threatening adverse drug experience
- Inpatient hospitalization or prolongation of existing hospitalization
- Persistent or significant incapacity or substantial disruption of the ability to conduct normal life functions
- A congenital anomaly/birth defect.
- Important medical events that may not result in death, be life-threatening, or require hospitalization may be considered a serious adverse drug experience when, based upon

Abbreviated Title: Anakinra in pustular dermatoses

Version Date: December 12, 2018

appropriate medical judgment, they may jeopardize the patient or subject and may require medical or surgical intervention to prevent one of the outcomes listed in this definition.

7.1.6 Disability

A substantial disruption of a person's ability to conduct normal life functions.

7.1.7 Life-threatening adverse drug experience

Any adverse event or suspected adverse reaction that places the patient or subject, in the view of the investigator or sponsor, at immediate risk of death from the reaction as it occurred, i.e., it does not include a reaction that had it occurred in a more severe form, might have caused death.

7.1.8 Protocol Deviation (NIH Definition)

Any change, divergence, or departure from the IRB-approved research protocol.

7.1.9 Non-compliance (NIH Definition)

The failure to comply with applicable NIH Human Research Protections Program (HRPP) policies, IRB requirements, or regulatory requirements for the protection of human research subjects.

7.1.10 Unanticipated Problem

Any incident, experience, or outcome that:

- Is unexpected in terms of nature, severity, or frequency in relation to
 - (a) the research risks that are described in the IRB-approved research protocol and informed consent document; Investigator's Brochure or other study documents, and
 - (b) the characteristics of the subject population being studied; **AND**
- Is related or possibly related to participation in the research; **AND**
- Suggests that research places subjects or others at a *greater risk of harm* (including physical, psychological, economic, or social harm) than was previously known or recognized.

7.2 NIH INTRAMURAL IRB AND CLINICAL DIRECTOR REPORTING

7.2.1 NIH Intramural IRB and NCI CD Expedited Reporting of Unanticipated Problems and Deaths

The Protocol PI will report in the NIH Problem Form to the NIH Intramural IRB and NCI Clinical Director:

- All deaths, except deaths due to progressive disease
- All Protocol Deviations
- All Unanticipated Problems
- All non-compliance

Reports must be received within 7 days of PI awareness via iRIS.

Abbreviated Title: Anakinra in pustular dermatoses

Version Date: December 12, 2018

7.2.2 NIH Intramural IRB Requirements for PI Reporting at Continuing Review

The protocol PI will report to the NIH Intramural IRB:

1. A summary of all protocol deviations in a tabular format to include the date the deviation occurred, a brief description of the deviation and any corrective action.
2. A summary of any instances of non-compliance
3. A tabular summary of the following adverse events:
 - All Grade 2 **unexpected** events that are possibly, probably or definitely related to the research;
 - All Grade 3 and 4 events that are possibly, probably or definitely related to the research;
 - All Grade 5 events regardless of attribution;
 - All Serious Events regardless of attribution.

NOTE: Grade 1 events are not required to be reported.

7.3 NCI Guidance for Reporting Expedited Adverse Events for Multi-Center Trials

The site PI must immediately report to the coordinating center PI any serious adverse event, whether or not considered drug related, including those listed in the protocol or investigator brochure and must include an assessment of whether there is a reasonable possibility that the drug caused the event within 24 hours of PI awareness of the event. The Site PI must also report any protocol deviations to the coordinating center PI within 7 days of PI awareness using the problem report form (See **APPENDIX L: CCR PROBLEM REPORT FORM**). A copy of this form can also be obtained from the NIAMS study coordinator. Participating centers must also submit the report to their IRB in accordance with their institutional policies.

7.4 DATA AND SAFETY MONITORING PLAN

7.4.1 Principal Investigator/Research Team

The clinical research team will meet weekly when patients are being actively treated on the trial to discuss each patient. Decisions about dose level enrollment and dose escalation if applicable will be made based on the toxicity data from prior patients.

All data will be collected in a timely manner and reviewed by the principal investigator or a lead associate investigator. Adverse events will be reported as required above. Any safety concerns, new information that might affect either the ethical and or scientific conduct of the trial, or protocol deviations will be immediately reported to the IRB using iRIS.

The principal investigator will review adverse event and response data on each patient to ensure safety and data accuracy. The principal investigator will personally conduct or supervise the investigation and provide appropriate delegation of responsibilities to other members of the research staff.

Abbreviated Title: Anakinra in pustular dermatoses

Version Date: December 12, 2018

7.4.2 Safety Monitoring Committee (SMC)

This protocol will require oversight from the Safety Monitoring Committee (SMC). Initial review will occur as soon as possible after the annual NIH Intramural IRB continuing review date. Subsequently, each protocol will be reviewed as close to annually as the quarterly meeting schedule permits or more frequently as may be required by the SMC. For initial and subsequent reviews, protocols will not be reviewed if there is no accrual within the review period. Written outcome letters will be generated in response to the monitoring activities and submitted to the Principal investigator and Clinical Director or Deputy Clinical Director, CCR, NCI.

8 STATISTICAL CONSIDERATIONS

The primary objective of this one-stage phase 2 study is to obtain an estimate of the response rate to treatment with anakinra for pustular dermatoses. Those patients who experience at least a 50% improvement in TBSAI will be considered responders. With 25 evaluable patients, the maximum width of a two-sided 95% confidence interval will be +/-20% if the response rate is 50%, and less wide if the response rate is either lower or higher than 50%. An early stopping rule will be implemented in order to guard against undue risk to enrolled subjects. If 0 of the first 9 patients fail to respond to anakinra therapy, there is a 95% probability that the true response rate is 28% or less, which is unacceptably low, and we will halt further patient recruitment.

All other biologic parameters will be evaluated using exploratory and descriptive methods, emphasizing non-parametric techniques.

It is anticipated that 1-2 patients per month may enroll onto this trial. In order to allow for a small number of unevaluable patients, the accrual ceiling will be set at 30 patients. Accrual would be estimated to last 18-24 months in order to enroll up to 30 patients.

